12.3 Interim Analyses

A blinded adaptive design to re-estimate the sample size for the stage 1 study is planned. The interim analysis to re-estimate the prevalence and the sample size is performed after 50% enrolled and measured study patients. Using the optimal sample size calculation (Stark and Zapf 2020), the sample size will be re-estimated based on the estimated prevalence. If the re-estimated sample size is larger than the size of the internal pilot study, recruitment continues until the re-estimated sample size is reached. The maximum sample size is set to 4,500 patients enrolled and measured.

Due to the blinded character of the adaptive design, no adjustment of the type I error rate is necessary [29].

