3.1 Background Information

After thyroid surgery, 0.6 to 4% of patients develop post-operative bleeding [3]. A recent opinion paper from British experts determines the average frequency at 2% [4], a recent meta-analysis found the rate of post-operative hemorrhage to be 1.48 % in 424,563 patients [5]. Only 40% of these complications occur within 8 hours [6] after of surgery while 90% of post-operative bleeding occurs within the first 48 hours [6]. In most cases, these are rapidly progressing complications that require immediate intervention, as the bleeding is caused by arterial bleeding sources [3, 6, 7, 8], recently shown by the correlation of increased cervical pressure and decrease in cerebral perfusion and cerebral oxygenation in an animal experimental series [9]. Although bleeding that occurs later must also be treated surgically, it usually progresses less rapidly. The risk factors for post-operative bleeding are male gender, arterial hypertension, subtotal resection procedures, the drugs acetylsalicylic acid and clopidogrel, other oral anticoagulants (NOAKs, coumarines etc.) and high blood loss during the procedure. However, available study data are too limited for being usable to reliably predict the risk of post-operative bleeding. There is also no evidence that early post-operatively bleeding is less severe than bleeding that occurs later in the course after the operation [10].

Although for thyroid surgery post-operative bleeding is significantly less common than recurrent nerve palsy or iatrogenic hypoparathyroidism [11], it is always a potentially fatal complication. Up to 0.6% of patients with post-surgical bleeding die, while others suffer from hypoxic brain damage [7]. The cause of death or of hypoxic brain damage in these patients is a lack of oxygen assumed to be caused by a cervical compartment syndrome. Thyroid surgery patients are mostly female (75%) and young. This makes serious complications such as post-surgical bleeding with its risk for additional morbidity and life-threatening consequences particularly tragic. Already 14.7% of women < 30 years of age and 33.4% of women between 31 and 45 years of age suffer from thyroid pathologies. More than 80% of thyroid surgeries are performed for benign diseases [12]. Such severe surgical complications with a potentially life-threatening outcome are therefore dispropor-

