12.2 Sample Size and Power Calculations

Initial sample size calculation for the stage 1 study is performed for the first primary hypothesis considering sensitivity and specificity as co-primary endpoints. This hypothesis states the superiority considering sensitivity and specificity of the IP against pre-defined minimum thresholds. The optimal sample size calculation for a single-arm confirmatory diagnostic accuracy study is applied [28].

The sensitivity of the IP is assumed to be 99%, the specificity is assumed to be 95%. The pre-defined minimum sensitivity equals 80%, the minimum specificity is 65%. A higher minimum sensitivity than minimum specificity is chosen as false negative results are much more relevant for the patient than false positive results. The assumed prevalence of clinically relevant hemorrhage within 48 hours following thyroid surgery is 1.5%. The two-sided significance level is set to 5% for the endpoint considering sensitivity and the endpoint considering specificity, respectively. An overall power of 80% is aimed. This leads to a total sample size of 1,470 patients enrolled and measured which is based on the assumed prevalence of 1.5%. Due to the optimal sample size calculation, the endpoint considering the sensitivity reaches a power of 86% and the endpoint considering the specificity a power of 98%. If the prevalence differs at least 22 events of clinically relevant hemorrhage within 48 hours following thyroid surgery need to be observed. Consecutive patient recruitment without any selection is important to receive valid estimates of predictive values as secondary endpoints.

The sample size calculations are performed with R version 4.0.2.

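### Section 12.3 stops recruitment at a projected patient number and does not carry over the 22-event minimum in section 12.2; at 1.5% prevalence about 41% of trials would end short of 22 events

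*Protocol*

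**What the plan says.** Protocol section 12.2 plans 1,470 enrolled and measured patients. It assumes sensitivity 99% against a minimum of 80%, specificity 95% against a minimum of 65%, and a 48-hour prevalence of 1.5%. On the error rate it says "The two-sided significance level is set to 5% for the endpoint considering sensitivity and the endpoint considering specificity, respectively"; its aim for the two endpoints jointly reads "An overall power of 80% is aimed". It gives a power of 86% for sensitivity and 98% for specificity, and then states the requirement in events: "If the prevalence differs at least 22 events of clinically relevant hemorrhage within 48 hours following thyroid surgery need to be observed".

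Section 12.3 plans one blinded re-estimation after 50% of patients are enrolled and measured. The new sample size is calculated from the prevalence estimated at that point. Then: "If the re-estimated sample size is larger than the size of the internal pilot study, recruitment continues until the re-estimated sample size is reached". Recruitment is capped at 4,500. The section does not mention 22 events, plans no second estimate and sets no floor at 1,470.

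**The concern.** The precision of the sensitivity estimate depends almost entirely on the number of bleeds. Section 12.2 recognises this by setting a minimum event count. Section 12.3 replaces that count with a patient number projected from roughly 11 events, an estimate with a relative standard error of about 1/√11 = 30%.

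The error has an awkward direction. A chance excess of bleeds in the first half shrinks the final sample, and the second half then returns to the true rate. For example, 15 events in 735 patients give N = 22 × 735 / 15 = 1,078. At a true 1.5% the remaining 343 patients yield about 5.1 more events, so about 20 in total. The trial would have followed 12.3 exactly and still missed the number that 12.2 says must be observed.

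**Working it through.** **Inputs.** From section 12.2: sensitivity 99% against 80%, two-sided 5%, prevalence 1.5%, 22 events, 1,470 patients. From section 12.3: one look at 50%, taken as 50% of 1,470 = 735 patients; lower bound equal to the pilot; cap 4,500. From section 3.1: a published range of 0.6 to 4% for post-operative bleeding, used here only to vary the prevalence.

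**Step 1: reproduce the plan.** The one-sample formula with null variance is

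power(n) = Φ{[(0.99 − 0.80)√n − 1.96√(0.80 × 0.20)] / √(0.99 × 0.01)}.

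- n = 22: (0.8912 − 0.7840)/0.0995 = 1.077, power 85.9% (stated 86%).
- n = 21: power 80.8%.
- n = 20: power 74.6%.

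Also 22/0.015 = 1,467 and 1,470 × 0.015 = 22.05. The stated figures reproduce, and on this formula power falls below the 80% aim at 20 or fewer events.

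**Step 2: the rule in 12.3.** Let X be the events among the first 735, X ~ Bin(735, p). The final number is N = min{4,500, max(735, ⌈22 × 735/X⌉)}, with N = 4,500 if X = 0. Later events follow Bin(N − 735, p). The form 22/observed prevalence is an inference; scaling by 22.05 instead moves the main result from 40.7% to 40.2%. Exact enumeration at p = 1.5% gives:

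| Quantity | Result |
|---|---|
| P(fewer than 22 events) | 40.7% |
| P(20 or fewer events) | 30.4% |
| P(fewer than 17 events) | 2.5% |
| Mean N | 1,624 |
| 5th to 95th percentile of N | 952 to 2,695 |
| Mean power for sensitivity | 83.8% |
| Mean power in trials ending below 22 | 67.8% |

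The re-estimated N falls below 1,470 in 42% of trials, and 67% of those end below 22 events.

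**Step 3: comparators at 1.5%.**

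| Rule | P(fewer than 22) | Mean N |
|---|---|---|
| Fixed 1,470, no re-estimation | 46.7% | 1,470 |
| Section 12.3 as written | 40.7% | 1,624 |
| Section 12.3 with a floor of 1,470 | 19.9% | 1,751 |
| Stop at the 22nd event, cap 4,500 | below 0.01% | 1,467 |

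The event-based stop has N between 996 and 2,012 (5th to 95th percentile). Its power is that of 22 events, 85.9%, with 1,624 − 1,467 = 157 fewer patients on average.

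**Step 4: other prevalences.**

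| True prevalence | P(<22), 12.3 | Mean N, 12.3 | P(<22), event stop | Mean N, event stop |
|---|---|---|---|---|
| 0.6% | 51.9% | 3,595 | 14.3% | 3,597 |
| 1.0% | 42.8% | 2,474 | <0.01% | 2,200 |
| 1.5% | 40.7% | 1,624 | <0.01% | 1,467 |
| 2.0% | 35.2% | 1,188 | <0.01% | 1,100 |
| 4.0% | 1.1% | 742 | <0.01% | 550 |

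**The case against.** **The two sections can be read together.** On this reading 12.2 sets the minimum and 12.3 only projects the number of patients likely to reach it, so a missing link sentence is the whole problem. That is a fair account of what may have been intended. But 12.3 states when recruitment ends, and that endpoint is a patient number. A trial team following it would stop with 20 events.

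**The re-estimation does not cause the shortfall.** A reader might infer that 12.3 makes matters worse. It does not: a fixed 1,470 misses 22 more often (46.7%) and has lower mean power (77.4% by the same formula). Falling short of an expected count is ordinary in any design that stops on patients. The fault is that 12.3 leaves most of the shortfall in place although 12.2 asks for a minimum.

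**Falling below 22 is not the same as failing.** This stands. Mean power meets the 80% aim, and 21 events still give 80.8%. On an exact binomial criterion power moves in steps: it is 84.3% at 17 events and 80.2% at 22, and success becomes impossible only below 17, which happens in 2.5% of trials. The protocol plans logit intervals from a mixed model, so neither formula is its actual test. The fairest measure of harm is the 30% of trials with 20 or fewer events, judged by the formula that reproduces the stated 86%.

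**The planning prevalence.** It is tempting to add that 1.5% is too high, because section 3.1 says "a recent meta-analysis found the rate of post-operative hemorrhage to be 1.48 % in 424,563 patients" and "90% of post-operative bleeding occurs within the first 48 hours", and 1.48% × 0.90 = 1.33%. The documents do not support this. The two figures come from different sources, and the time window of the first is not given. The same section also cites an average of 2% and a range of 0.6 to 4%; 2% × 0.90 would be 1.8%. The cited figures lie on both sides of 1.5%.

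**Conclusion.** The concern holds as an unreconciled pair of rules with a measurable consequence. Section 12.3 as written does not deliver the minimum stated in 12.2: about 41% of trials end below 22 events at the planning prevalence, from about 52% at 0.6% to about 1% at 4%. The cost in power lies in the lower tail, not in the average.

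The figures rest on three assumptions: the interim look falls at 735 patients, the new N is 22 divided by the observed prevalence, and no unwritten floor of 1,470 applies. With such a floor the shortfall would still be about 20%.

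Two stronger conclusions do not follow. The trial as a whole is not underpowered by this rule at 1.5%. An event-based stop would not secure 22 events in every case either, because the 4,500 cap can bind when bleeding is rare.

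**What to change.** State in section 12.3 that recruitment continues until 22 confirmed hemorrhages within 48 hours have occurred or 4,500 patients have been enrolled and measured, whichever comes first. Take the count from the reference standard only, blinded to pressure data. The interim prevalence estimate can stay as a projection of the expected final number, for planning sites and supplies.

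The change is protocol wording. Device readings are already hidden from users (sections 7.1.1 and 7.2), and adjudication is already planned as a continuous online process (section 15.1.3), so the count needs no new machinery.

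There are two downsides. The final number is not known in advance, but that is already so under 12.3. Recruitment may also overrun while events are adjudicated. Planned accrual is 1,470/12 ≈ 122 patients a month, so if confirmation lagged by one month (an assumption; the protocol gives no figure), the overrun would use up most of the average saving of 157 patients at 1.5%. At 0.6% there is no saving, and about 14% of trials would reach the cap with fewer than 22 events, so the text should say how that outcome will be reported.

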12.4 Patient Selection for Analyses

A patient is considered as enrolled into the current trial according to regulatory requirements as soon as the signed the informed consent form. All enrolled patients will be part of the safety population.

A patient is considered as measured as soon as he is enrolled, screened, index thyroid surgery as defined in the study protocol was performed, and pressure monitoring by the IP was started. All measured patients will be part of FAS and will be followed according to study protocol.

Refer to section 6.2.1 for additional details.

13. Access to Source Data / Documents

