6.2 Study Population

6.2.1 Number of patients and definition of status

HEDOS will enrol and measure presumably 1,470 eligible adult patients and follow each of them for 1 month, assuming that 22 events of clinically relevant hemorrhage within 48 hours following thyroid surgery will be observed.

A patient is considered as enrolled into the trial according to regulatory requirements as soon as he has **signed** the informed consent form. Documentation of any patient data in the e-CRF is permitted only after the patient signs the informed consent form. All enrolled patients will be reported and will be part of the safety population. Enrolled patients who are subsequently not measured with thyroid surgery as defined in the study protocol will not count to the number of enrolled patients needed, and will be replaced as soon as absence of thyroid surgery has been determined and documented in the clinical files of the patient.

A patient is considered as **screened** as soon as inclusion and exclusion and other eligibility criteria have been checked and documented in the e-CRF after the patient signed the informed consent form. Screened patients who are subsequently not measured with thyroid surgery as defined in the study protocol will not count to the number of enrolled patients needed, and will be replaced as soon as absence of thyroid surgery has been determined and documented in the clinical files of the patient. These patients will be followed until date of determination of absence of thyroid surgery. If a screened patient is scheduled for index thyroid surgery after global end of the study or after termination of study participation of the corresponding study site his study participation will end at the corresponding date of administrative termination. A patient is considered as measured in the trial as soon as he is **enrolled and thyroid surgery** as defined in the study protocol was performed. All measured patients will be part of the ITD population. Measured patients will be followed according to study protocol.

The day of **enrolment** is **day 1 of study participation**, the **day of index thyroid surgery** as defined in the study protocol is **day 1 of follow-up** for primary and secondary endpoints of an individual study patient.

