12.1.2 Analysis of the primary endpoint

Analyses of the co-primary endpoints in the stage 1 diagnostic study are based on the population of all enrolled patients with subsequent index thyroid surgery. This corresponds to the intention to diagnose (ITD) principle, whereas missing or inconclusive values are imputed by false positive or false negative results, respectively [25]. In accordance with the ICH E9 guidelines, the analysis population of all these patients is defined as the "Full Analysis Set" (FAS).

In the first pair of primary hypotheses, sensitivity and specificity are considered as co-primary endpoints. They are combined via the Intersection-Union Test. The global null hypothesis can only be rejected if both individual null hypotheses of sensitivity and specificity are rejected. The corresponding first global alternative hypothesis states that the IP exceeds a pre-defined minimum sensitivity of 80% and specificity of 65%. The second primary global hypotheses, the second primary global hypothesis can only be evaluated in a confirmative way if the first global primary hypothesis leads to a significant result. The hierarchical order of hypotheses requires no adjustment of the type I error rate.

The analysis of the first global primary hypothesis contains the estimation of the resulting sensitivity and specificity of the IP according to the defined cut-off value of 12 mmHg. For the estimation, a mixed binary logistic regression model is used [26]: The binary test result represents the dependent variable, the true disease status is included as fixed effect. Additionally, a random-intercept is estimated for each centre. Sensitivity is estimated via the calculation of the marginal mean for a diseased individual (=surgical intervention performed which confirmed post-operative hemorrhage needing intervention). False-positive rate, which is the counter probability of the specificity, is estimated via the calculation of the marginal mean for a non-diseased individual. Twosided 95%-logit confidence intervals with p-values are reported.

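### Section 12.4 makes the start of pressure monitoring a condition for the FAS, while the Summary, 6.2.1 and 12.1.2 include every operated patient, so patients whose monitoring never started are errors under one rule and absent under the other

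*Protocol*

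**What the plan says.** The protocol defines the primary analysis population in several places.

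- **Section 12.1.2** (and, in the same terms, the Summary): the co-primary analysis is "based on the population of all enrolled patients with subsequent index thyroid surgery". The section calls this intention-to-diagnose (ITD) and adds that "missing or inconclusive values are imputed by false positive or false negative results, respectively". It then says that "the analysis population of all these patients is defined as the" Full Analysis Set (FAS).
- **Section 6.2.1**: a patient is *measured* once enrolled and operated on. No device condition is attached, and "All measured patients will be part of the ITD population".
- **Section 12.4**: a patient is *measured* once enrolled, screened, "index thyroid surgery as defined in the study protocol was performed, and pressure monitoring by the IP was started". The section continues: "All measured patients will be part of FAS and will be followed according to study protocol". It closes with "Refer to section 6.2.1 for additional details", although 6.2.1 defines the term differently.

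Sections 12.2 and 12.3 express the sample size of 1,470, the 50% interim trigger and the cap of 4,500 in enrolled and measured patients.

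**The concern.** *Measured* and *FAS* each carry two incompatible meanings in the current text. They part over one group: operated patients in whom recording never began. Such a patient has no index-test result at all, which is the plainest case the ITD imputation rule exists to cover. Under 12.1.2 the patient is scored as a wrong result; under 12.4 the patient is not in the analysis.

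Two things are at stake. The first is the sensitivity test, which rests on about 22 bleeds, so that a single patient matters. If the choice of definition is still open when the recordings are unsealed, the primary population could be chosen with knowledge of the result. The second is conduct: the recruitment target, the interim trigger and the cap all count measured patients. The replacement rule in 6.2.1 covers only absence of surgery, so under 12.4 a non-started patient would not count towards 1,470 and no rule would replace that patient.

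**Working it through.** **Inputs.** From sections 12.1.2 and 12.2: assumed sensitivity 99% and specificity 95%; minimum values 80% and 65%; two-sided 5%; prevalence 1.5%; N = 1,470; success if both lower 95% limits exceed the minimum values. The non-start rate *f* is not in the protocol and is assumed here at 1%, 3% and 5%, the same in bleeders and non-bleeders.

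**1. The plan's own figures.** Events: 1,470 × 0.015 = 22.05, so 22. Power for sensitivity by the normal approximation:

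Φ[(0.99 − 0.80 − 1.96·√(0.80·0.20/22)) / √(0.99·0.01/22)] = Φ[(0.190 − 0.167)/0.0212] = 0.859.

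This matches the stated 86%.

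**2. One bleeder with no started recording, the other 21 detected.**

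| Definition | Counted as | Exact lower 95% limit | Against 80% |
|---|---|---|---|
| 12.1.2 / 6.2.1 | 21/22 | 77.2% | fails |
| 12.4 | 21/21 | 0.025^(1/21) = 83.9% | passes |

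A simple logit interval for 21/22 gives 73.9%, so that result fails on either interval. For 21/21 the simple logit interval is undefined, and with a correction of 0.5 its lower limit is 72.3%. The pass under 12.4 is therefore shown for the exact interval only.

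**3. How far the one-patient reversal extends.** With one miss, the exact lower limit is 79.6% for 24/25 and 80.4% for 25/26. On exact limits, one miss is fatal up to 25 bleeds and tolerable from 26. On the simple logit interval the change comes later. The lower limit is 79.8% for 29/30. For 30/31 the logit is ln 30 = 3.401 with standard error √(1/30 + 1) = 1.017; the lower bound 3.401 − 1.96 × 1.017 = 1.409 corresponds to 80.4%.

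**4. Chance of success at 22 bleeds, exact rule (all 22 detected).** With non-starts scored as misses, effective sensitivity is 0.99(1 − *f*) and the chance is [0.99(1 − *f*)]^22. Effective specificity is 0.95(1 − *f*).

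| *f* | Non-starts among 1,470 | Effective sensitivity | Chance of 22/22, scored as misses | Effective specificity |
|---|---|---|---|---|
| 0 | 0 | 99.0% | 80% | 95.0% |
| 1% | 15 | 98.0% | 64% | 94.1% |
| 3% | 44 | 96.0% | 41% | 92.2% |
| 5% | 74 | 94.1% | 26% | 90.3% |

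If non-started bleeders are dropped instead, the chance that every remaining bleeder is detected stays at 80% to 81% at all these rates. The 80% baseline is 0.99^22 under the exact rule; it differs from the plan's 86% because that figure comes from the normal approximation.

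**The case against.** Three places agree, one of them the section that governs the primary analysis, and 12.4 itself points back to 6.2.1. One could call 12.4 an outlying sentence that no analyst would follow. Section 6.2.4 also says that every eligible operated patient will receive the device, so the two sets coincide unless something goes wrong. This limits how often the conflict would matter, but not what happens when it does: 12.4 is headed as the section on patient selection for analyses, and it names the FAS.

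A reader might infer that 12.4 removes device failures in general. It does not. Once monitoring has started, a failure stays in the set and falls under the imputation rule in 12.1.2 or the censoring rule in 4.1.

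A reader might also treat every non-start as the device's fault. The protocol does not say why monitoring might not start, and some reasons may have nothing to do with the device, such as a probe that was never placed or a withdrawal of consent. The gain in accuracy under 12.4 is therefore a gain relative to the ITD quantity, and not shown to be bias among patients actually tested. Even so, the imputation rule in 12.1.2 makes no exception by cause.

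The exact interval is not the planned one, 22 events is a minimum, and re-estimation can take enrolment up to 4,500. All of that stands and narrows the size of the claim.

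**Conclusion.** The contradiction is real and lies in the current text. Following 12.4 drops missing results that 12.1.2 sets out to penalise, and it changes who counts towards the target, the interim trigger and the cap.

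For sensitivity, at about 22 bleeds one non-started bleeder can reverse the conclusion. A reader might infer that one patient would always decide the trial. That is not supported: the reversal is demonstrated with exact limits at about 22 to 25 events, and the planned model-based logit interval will behave differently. The fall in the chance of 22/22 from 80% to between 64% and 26% rests wholly on assumed non-start rates of 1% to 5%.

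Nor is specificity threatened. At 90% to 94% over the same range it remains far above 65%.

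**What to change.** In section 12.4, delete two conditions from the definition of *measured* and the FAS: that the patient was screened, and that pressure monitoring by the IP was started. Removing only the second would still leave 12.4 different from 6.2.1 and 12.1.2. With both gone, the FAS is all enrolled patients with index thyroid surgery throughout, and the target of 1,470, the 50% trigger and the cap of 4,500 have one meaning.

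Keep monitoring started as the criterion for a separately named supportive set, so that accuracy among patients with a recording can be reported beside the primary result. Make the change before the recordings are opened.

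The edit is short, but it has a price. If non-starts occur, the sensitivity estimate and the chance of success become less favourable, possibly by a good deal on the figures above. Section 12.2 should therefore state whether the assumed 99% sensitivity already allows for non-starts; if it does not, the sample size should be checked against an explicit non-start rate.
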